5.4.2. Additional consideration

In addition to above planned analysis for RTI and LRTI, following additional analysis is planned: -

- Descriptive analysis on maximum viral load per subject based on qRT-PCR confirmed RSV infection of maximum severity will be performed.
- Listing will be presented for all cases of RSV infection at Day 731 with the details of gender, age at episode, country, site, day of event (i.e days since first visit), classification according to maximum severity of episode as RSV RTI/RSV LRTI/ RSV severe LRTI and RSV very severe LRTI, RSV hospitalization ‘Yes/No’, SpO₂ value, respiratory rate, result of RSV qRT-PCR and RVP result will be presented.
- Listings will be generated at Day 731 for all hospitalized cases with gender, age at episode, classification according to maximum severity of episode as (RSV RTI/RSV LRTI/ RSV severe LRTI and RSV very severe LRTI), RVP result, total number of calendar days on which the child was hospitalized, days requiring monitoring/nursing observation, days requiring nasogastric or intravenous fluids, days requiring supplemental oxygen, days requiring respiratory support excluding mechanical ventilation, days requiring mechanical ventilation and days requiring pediatric intensive care unit management.

6. ANALYSIS INTERPRETATION

For the occurrence of very severe RSV-LRTI among RSV infected infants with a negative RSV exposure status (at screening based on in-stream baseline serological testing) from first vaccination (Day 1) up to the end of the first RSV transmission season, if the upper boundary of the 95% one-sided lower CI of the rate is under 80%, it indicates that the very severe RSV-LRTI rate is less than that of the historic RSV-FI trials [Kim, 1969].

Comparative analyses will be exploratory and should be interpreted with caution considering that there is no adjustment for multiplicity and that group sizes are small for these comparisons.

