3.2.2. Secondary endpoints

- Occurrence of RSV-RTI, RSV-LRTI, severe RSV-LRTI and very severe RSV-LRTI (according to standardized case definitions) as from first vaccination (Day 1) up to the end of the first RSV transmission seasons.
- Occurrence of RSV-RTI, RSV-LRTI, severe RSV-LRTI and very severe RSV-LRTI (according to standardized case definitions) as from first vaccination (Day 1) up to the end of the second RSV transmission seasons.
- Occurrence of SAEs from first vaccination (Day 1) up to the end of the second RSV transmission seasons.
- Occurrence of RSV-LRTI (AE of special interest) as from first vaccination (Day 1) up to the end of the first RSV transmission season, and up to the end of the second RSV transmission seasons.

- Occurrence of very severe RSV-LRTI (according to standardized case definitions) among RSV infected infants with a negative RSV exposure status (at screening based on in-stream baseline serological testing) from first vaccination (Day 1) up to the end of the first RSV transmission seasons.
- Humoral response to the investigational RSV vaccine, pre-vaccination (Screening), post-Dose 1 (Day 31) and post-Dose 2 (Day 61 and at the end of the first RSV transmission season):
 - Neutralizing antibody titers against RSV-A
 - RSV F antibody concentrations

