5.4. Analysis of RTI and LRTI

5.4.1. Analysis of RTI and LRTI planned in protocol

The primary analysis will be performed on the ES of subjects with a negative RSV exposure status (at screening based on in-stream baseline serological testing) in the pooled single dose RSV vaccine group, the pooled two dose RSV vaccine group, and the pooled comparator group separately for first and second RSV seasons and overall. A similar analysis will be performed on the entire ES. As primary analysis, the assessment of RSV infection will be performed using the quantitative RT-PCR according to standardized case definitions (see Table 6 of the SAP) based on the available WHO case definitions.

The number of RSV infections within each group and the maximum disease severity of the event will be tabulated. The rate (with 95% CI) of RSV-RTI and RSV-LRTI and infections progressing to hospitalization will be evaluated for each of the three pooled groups.

The rate of very severe RSV-LRTI among RSV infected infants with a negative RSV exposure status (at screening based on in-stream baseline serological testing) from first vaccination (Day 1) up to the end of the first RSV transmission season will be estimated as well as 95% one-sided lower CI.

The proportion and the relative risk of subjects with at least one RSV-associated RTI (with 95% CI) between each of two pooled RSV vaccine groups and the pooled control group will be calculated for both the cohort of subjects with a negative RSV exposure status (at screening based on in-stream baseline serological testing) on the ES and on the entire ES. The same descriptive analysis will be performed for subjects with at least one RSV-associated LRTI and those with at least one RSV-associated severe LRTI.

Descriptive analyses (mean, median, min, max) of viral load assessed by the quantitative RT-PCR (RSV-A/B) of all cases as listed in Table 6 of the SAP will be tabulated by case category. This analysis will also be done on the three pooled groups.

The incidence rate of all cases as listed in Table 6 of the SAP (with 95% CI) will be calculated by the three pooled groups. The same descriptive analysis will be performed for all cause LRTI and all cause severe LRTI. These will also be presented for each viral etiology identified by the multiplex PCR.

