The incidence rate of asymptomatic RSV infections (with 95% CI) detected by the quantitative PCR (RSV-A/B), will be tabulated by the three pooled groups. Descriptive analyses (mean, median, min, max) of viral load assessed by the quantitative RT-PCR (RSV-A/B) of those asymptomatic RSV infections will also be done on the three pooled groups.

The RVP (Multiplex PCR) on specimens from all RSV-A/B positive and confirmed LRTI cases, according to case definition presented in Table 6 (Figure 3 of the protocol for the decision tree), will be tabulated as a qualitative assessment profiling the potential co-infections occurring in these subjects.

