N= number of subjects with at least one RSV infection (symptomatic or asymptomatic)

n/% = number/percentage of subjects reporting at least one RSV hospitalization

95%CI= Exact 95% confidence interval; LL = lower limit, UL = upper limit

Template 41 Number and percentage of subjects reporting the RSV infection of different severity (based on WHO case definition) by number of events experienced between vaccination dose 1 up to end of <first, second> RSV season for pooled RSV 1D, RSV 2D and Comparator/Placebo group <Exposed Set, Exposed Set with negative RSV baseline status>

Characteristics	Categories	<Each group> N=xx				
		n	%	95% CI	LL	UL
RSV infection-symptomatic or asymptomatic*	0					
	1					
	2					
RSV-RTI	0					
	1					
RSV-LRTI	0					
	1					
	2					
RSV-Severe LRTI	0					
	1					
RSV-very severe LRTI	0					
	1					
All cause LRTI	0					
	1					
	2					
	3					
RSV hospitalization\$	0					
	1					
	2					
	3					

Short group label = long group label

N = number of subjects in each group

n = number of subjects in a given category

% = $100 * n / N$

LL, UL for percentage = Exact 95% Lower and Upper confidence limits

Please note – Single episode can be considered in multiple category depending on the symptom experienced

* Association to RSV based on central testing only for asymptomatic visit (no local test available)

\$Confirmed RSV infection and hospitalized for acute medical condition

Template 42 Number and percentage of RSV infections and associated disease severity (based on WHO case definition) and relative risk from vaccination dose 1 up to end of <first, second> RSV season for pooled RSV 1D, RSV 2D and Comparator/Placebo group <Exposed Set, Exposed Set with negative RSV baseline status>

Categories	<Each Group> N =		Relative risk (RSV1D vs Comparator/Placebo)				Relative risk (RSV2D vs Comparator/Placebo)			
			95% CI		95% CI				95% CI	
	n	%	LL	UL	Values	LL	UL	Values	LL	UL
RSV asymptomatic (Excluding RSV-RTI, LRTI, RSV-severe LRTI or RSV-very severe LRTI)										
RSV RTI (Excluding LRTI, RSV-severe or very severe LRTI)										
RSV LRTI (Excluding RSV-severe or very severe LRTI)										
RSV-severe LRTI (Excluding RSV-very severe LRTI)										
RSV-very severe LRTI										

Short group label = long group label

* Association to RSV based on central testing only for asymptomatic visit (no local test available)

N = number of RSV positive samples in each group

n** = number of cases in each category

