RSV-ve = Subject are RSV negative at baseline

Template 56 Summary of subjects by unsolicited adverse event category with onset within 30 days of first and second vaccination (Exposed Set)

	<Group 1> N=XXXX				<Group 2> N=XXXX			
			95% CI				95% CI	
	n	%	LL	UL	n	%	LL	UL
At least one unsolicited adverse event	xxx	xx.x	xx.x	xx.x	xxx	xx.x	xx.x	xx.x
At least one related unsolicited adverse event	xxx	xx.x	xx.x	xx.x	xxx	xx.x	xx.x	xx.x
At least one grade 3 unsolicited adverse event	xxx	xx.x	xx.x	xx.x	xxx	xx.x	xx.x	xx.x
At least one grade 3 related unsolicited adverse event	xxx	xx.x	xx.x	xx.x	xxx	xx.x	xx.x	xx.x
At least one medically attended unsolicited adverse event	xxx	xx.x	xx.x	xx.x	xxx	xx.x	xx.x	xx.x

Any adverse event = at least one adverse event experienced (regardless of the MedDRA Preferred Term)

N = number of subjects with at least one administered vaccination

n/% = number/percentage of subjects reporting the adverse event at least once

95% CI = exact 95% confidence interval; LL = Lower Limit, UL = Upper Limit

Template 57 Number and percentage of subjects with at least one RSV-RTI progressing to RSV-LRTI, RSV-severe LRTI, RSV-very severe LRTI and RSV hospitalization from vaccination dose 1 up to end of <first, second> RSV season for pooled RSV 1D, RSV 2D and Comparator/Placebo groups <ES, Exposed Set with negative RSV exposure status>

Categories	<each group> N =				Total N =			
			90% CI				90% CI	
	n	%	LL	UL	n	%	LL	UL
RSV-LRTI								
RSV-severe LRTI								
RSV-very severe LRTI								
RSV hospitalization*								

<Blinded = Blinded group>

<RSV 1D = Pooled 1D RSV>

<RSV 2D = Pooled 2D RSV>

<COMP_PLB = Pooled comparator or placebo>

* Confirmed RSV infection and hospitalized for acute medical condition

N = number of subjects with at least one RSV-RTI infection

n/%= number/percentage of subjects reporting at least once the symptom

90%CI= Exact 90% confidence interval; LL = lower limit, UL = upper limit

Please note – Single episode is considered in single category of highest severity based on the symptom experienced

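### The 80% rule for very severe RSV-LRTI is set among RSV-infected infants, but the only table with a matching interval divides by infants with RSV-RTI, and the confidence limit is mislabelled

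*SAP*

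**What the plan says.** The secondary endpoint in SAP section 3.2.2 is "Occurrence of very severe RSV-LRTI (according to standardized case definitions) among RSV infected infants with a negative RSV exposure status", from dose 1 to the end of the first season. Section 5.4.1 says that this rate "will be estimated as well as 95% one-sided lower CI". Section 6 restates the same population ("For the occurrence of very severe RSV-LRTI among RSV infected infants with a negative RSV exposure status") and concludes that the rate is below that of the cited historic trials "if the upper boundary of the 95% one-sided lower CI of the rate is under 80" per cent.

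Infection is not limited to symptomatic disease. Section 5.4.1 plans to tabulate "The incidence rate of asymptomatic RSV infections (with 95% CI) detected by the quantitative PCR (RSV-A/B"), and the footnote to Template 40 defines its denominator as "N= number of subjects with at least one RSV infection (symptomatic or asymptomatic").

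Template 57 reports very severe RSV-LRTI with an exact 90% interval. Its footnote reads "N = number of subjects with at least one RSV-RTI infection".

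**The concern.** Section 6 calls the comparative analyses exploratory, so the 80% rule is the one numerical criterion in the SAP from which a conclusion is drawn. A programmer looking for the output that feeds it would reach Template 57, because the upper limit of an exact two-sided 90% interval is the one-sided 95% upper limit. That table divides by a subset of the infants named in the endpoint. Section 5.4.1, which specifies the analysis, does not mention an upper limit at all.

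Section 7.1 unblinds the statistician at the Day 61 analysis, before the first-season data are complete. If the denominator and the limit are not fixed in the SAP, they may be settled by someone who can see treatment assignments.

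**Working it through.** **Which table gives the tested quantity?** The rule needs subjects with very severe RSV-LRTI divided by subjects with any confirmed RSV infection, in the RSV-negative Exposed Set, for the first season, with a one-sided 95% upper limit. The candidates in section 13 are:

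- Template 39: very severe RSV-LRTI by subject, but divided by all exposed subjects.
- Template 40: the right denominator, but hospitalization only, with a 95% interval.
- Template 42: severity categories, but N is RSV-positive samples, with 95% intervals.
- Template 45: N is RSV-positive subjects, but it reports viral load and no proportion.
- Template 57: very severe RSV-LRTI by subject with an exact 90% interval, but N is subjects with RSV-RTI.

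None gives it.

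**Who is lost from Template 57?** In Table 6, RSV-RTI needs a runny nose, a blocked nose or a cough. Symptomless infections are therefore outside N. RSV-LRTI can be reached through cough or difficulty breathing, so an infant with difficulty breathing and none of the three RSV-RTI symptoms can be a very severe case and still be left out.

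**Formulae.** Section 10.1.3.20 prescribes Clopper-Pearson intervals. For x cases in n subjects, the one-sided 95% upper limit is U = the 0.95 quantile of Beta(x + 1, n − x). The exact two-sided 90% interval has the same upper limit. For 5/10 both are 77.8%, while the two-sided 95% upper limit is 81.3%, so the interval level alone can decide the rule.

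**Effect of the denominator.** The SAP states no expected number of infections or cases for this rule, so there is no planned figure to reproduce, and all counts below are assumed.

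| Very severe cases | All infected: n, U | RSV-RTI only: n, U | Under 80%? |
|---|---|---|---|
| 6 | 12, 75.5% | 10, 85.0% | yes / no |
| 4 | 10, 69.6% | 8, 80.7% | yes / no |
| 2 | 10, 50.7% | 5, 81.1% | yes / no |
| 3 | 20, 34.4% | 14, 46.6% | yes / yes |

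Dropping symptomless infants keeps x and lowers n, so U rises. Leaving out a very severe case who had difficulty breathing alone lowers both x and n and acts the other way: 6/10 gives 85.0% and 5/9 gives 83.1%.

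**Effect of the label.** A lower limit is L = the 0.05 quantile of Beta(x, n − x + 1), which for x = n is 0.05^(1/n). If L were compared with 80%, 13 cases in 13 infants would pass, since 0.05^(1/13) = 79.4%.

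**How little information can satisfy the rule.** For x = 0, U = 1 − 0.05^(1/n). With n = 2 this is 1 − 0.2236 = 77.6%, so 0/2 meets the rule. So does 12/20, at 78.3%. The conclusion cannot be read without the number infected.

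**The case against.** Several stronger readings are tempting, and the SAP does not support them.

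- A reader might infer that the rule can never be met, because a lower-limit interval runs up to 100%. Section 6 compares the upper boundary with 80%, an interval from 0 to U is sometimes called a lower interval, and Template 57's 90% level fits that reading. The intent is recoverable. What stands is that section 5.4.1 lacks the clarification.
- A reader might infer that Template 57's numerator is not contained in its denominator. Its title restricts the table to subjects whose RSV-RTI progressed, so the fault is possible omission of a case.
- A reader might infer that the rule could be read from Template 57's Total column. Section 5.4.1 already requires the pooled one-dose, two-dose and comparator groups separately. Section 6 does not repeat this, but a Total column does not make Total the decision population.
- A reader might infer false reassurance. Dropping symptomless infections makes the rule harder to meet.

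It is also fair to say that no text ties Template 57 to the rule. Section 10.2 leaves the flagging of tables for each analysis to a table of contents that is not shown. Template 39 already plans both counts, infected subjects and very severe cases, in the right set and by pooled group, so only their ratio and its limit are missing. However, section 10 says that all applicable templates are in section 13, and none of them supplies that ratio.

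The numerical examples are assumed. With 8 to 20 infected infants, of whom at least half have RSV-RTI, every reversal examined needs an observed very severe rate of 20% or more among the infected. Only with very few infections do reversals occur at lower rates (0/2 gives 77.6%, 0/1 gives 95.0%).

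**Conclusion.** Wrong as written, and should be fixed. The endpoint, the analysis text and the rule all use RSV-infected infants. The only subject-level very severe table with a fitting interval uses RSV-RTI subjects, and section 5.4.1 names the wrong side of the interval.

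The mismatch can reverse the conclusion (75.5% against 85.0% at 6 cases), mostly in the conservative direction. At low very severe rates with a reasonable number infected it does not (34.4% against 46.6%). How often it would matter depends on the number infected, the share without symptoms and the very severe rate, none of which the SAP gives. The denominator and label faults themselves rest on the text alone.

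The weight is limited. This is a secondary endpoint, section 6 treats the result as an indication, and no action in the SAP follows from it.

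**What to change.** 1. In sections 5.4.1 and 6, replace the one-sided wording with: one-sided 95% Clopper-Pearson upper confidence limit (the upper limit of the exact two-sided 90% CI).
2. Add a very severe RSV-LRTI row to Template 40 with the exact 90% interval, and widen its title and footnote to match. N is subjects, not infections: those with at least one qRT-PCR-confirmed RSV infection, with or without symptoms, in the Exposed Set with negative RSV exposure status, from dose 1 to the end of the first season. Template 40 is laid out by group and has no Total column. Template 57 can stay as a description of progression from RSV-RTI.
3. In section 6, state that the rule is read for RSV 1D and RSV 2D separately and not from a Total column, with the number of infected subjects and the comparator rate shown beside each result.

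The cost is a few sentences and one table row. No new data are needed, because Template 39 already calls for both counts.

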7. CONDUCT OF ANALYSES

7.1. Sequence of analyses

The statistical analyses will be performed in 3 steps:

- An analysis will be performed when all data up to Day 61 are available. Additional safety data available at the time of this analysis will be described. At this point, the statistician will be unblinded (i.e., individual subject treatment assignments will be available) and the study will be conducted in a single blind manner, with patients remaining blinded up to the last study visit (end of the second RSV transmission season). Summary results may unblind some specific subjects, but no individual listings will be provided and the investigator will not have access to the treatment

allocation up to the last study visit (end of the second RSV transmission season), except in case of emergency unblinding (see Section 9.8 of the protocol)

- An analysis will be performed when all data up to Visit 7 (end of the first RSV transmission season, i.e., data that are as clean as possible) are available. No individual listings will be provided.
- The final analysis will be performed when all data up to study conclusion (end of the second RSV transmission season) are available. An integrated clinical study report containing all data will be written and made available to the investigators at that time.

If the data for tertiary endpoints become available at a later stage, (an) additional analysis/ analyses will be performed. These data will be documented in annex(es) to the study report and will be made available to the investigators at that time.

Description	Disclosure Purpose (CTRS=public posting, SR=study report, internal)
Day 61 analysis	Internal, web disclosure
End of RSV season 1	Internal
End of RSV season 2	Web disclosure, Study report

7.2. Statistical considerations for interim analyses

No interim analyses are planned

8. CHANGES FROM PLANNED ANALYSES

Following are few changes from planned analysis:-

- In the protocol, we have PPS up to Day 61 which included Day 31 as well. To have better clarity with respect to PPS for Day 31, the text has been re-worded for the definition of PPS population. PPS has also been defined for Day 31 timepoint along with PPS at Day 61 and end of 1st RSV transmission season. Also, as the timepoint 'End of 1st RSV transmission season is not exactly Day 365, so the Day 365 has been removed and only kept as PPS at end of 1st RSV transmission season. The criteria of eliminating subject from the PPS of respective timepoint is accordingly reworded.
- In the protocol amendment 3, it is mentioned under Analysis of Immunogenicity section that 'In summary table on the Adapted PPS for immunogenicity, PPS for immunogenicity at Day 61 will be used for Pre, Day 31 and Day 61 immunogenicity summary and PPS for immunogenicity at Day 365 for Day 365 immunogenicity summary.' As we have added the PPS for Day 31 in the SAP, accordingly the summary table presentation has been modified as 'In summary table on the Adapted PPS for immunogenicity, immunogenicity summary result at Day 31, Day 61 and end of first RSV transmission season) will be based on PPS of Day 31, Day 61 and end of first RSV transmission season, respectively'.
- Table to present percentage of responders in terms of neutralizing antibody titers with 95% CI has been removed as there is no definition of response available.

9. NON-STANDARD DATA DERIVATION RULES AND STATISTICAL METHODS

The following sections describe additional derivation rules and statistical methods which are not presented in section 10.1 (Business rules for standard data derivations and statistical methods).

9.1. Immunogenicity

- Assay cut-off for the humoral immunity will be per the following table

Component	Method	Unit	Cut-off
Respiratory Syncytial Virus A Ab	NEUTRALIZATION	ED60	18
Respiratory Syncytial Virus F protein Ab.IgG (Anti-RSV PreF antibody)	ELISA	EU/ml	10
Respiratory Syncytial Virus F protein Ab.IgG (Palivizumab competing Ab)	ELISA	µg/ml	9.6

- For RSV neutralizing assay, the LLOQ and ULOQ is set at 18ED60 and 21654 ED60. For analysis, the cut-off is set at the lower limit of quantification. For results below the cut-off, an arbitrary value of half of the cut-off will be considered for calculation of GMC and fold increase. The result above the ULOQ is set at ULOQ for analysis.
- For anti-RSV PreF antibody and RSV PCA, the cut-off is set at the level of detection. For results below the cut-off (LOD), an arbitrary value of half of the cut-off will be considered for calculation of GMC and fold increase.

9.2. RTI and LRTI

During the analysis of the study, all cases identified during the surveillance of RSV-RTI will be definitively classified as either RTI, LRTI, severe LRTI or very severe LRTI according to the standardized case definitions (Table 6 in the SAP) based on the available World Health Organization (WHO) case definitions (Table 6 in the protocol)

Table 6 Case definitions for data analysis

Case	At sea level up to 2500 meters elevation	Above 2500 meters elevation
RSV-RTI	Runny nose OR blocked nose OR cough AND Confirmed RSV infection ⁴	Same
RSV-LRTI	History of cough OR difficulty breathing ¹ AND SpO ₂ < 95% ² , OR RR increase ³ AND Confirmed RSV infection ⁴	Same but with SpO₂ < 92%
severe RSV-LRTI	Meeting the case definition of RSV-LRTI AND SpO ₂ < 93% ² , OR lower chest wall in-drawing	Same but with SpO₂ < 90%
very severe RSV-LRTI	Meeting the case definition of RSV-LRTI AND SpO ₂ < 90% ² , OR inability to feed, OR failure to respond / unconscious	Same but with SpO₂ < 88%

Case	At sea level up to 2500 meters elevation	Above 2500 meters elevation
RSV hospitalization	Confirmed RSV infection ⁵ AND Hospitalized for acute medical condition ⁶	Same
All-cause LRTI	History of cough OR difficulty breathing ¹ AND SpO ₂ < 95% ² , OR RR increase ³	Same but with SpO₂ <92%

LRTI = lower respiratory tract infections; RR = respiratory rate; RTI = respiratory tract infections; SpO₂ = blood oxygen saturation.

¹ Based on history reported by parents.

² The lowest value during the course of illness will be used.

³ RR increase defined as:≥ 50/minute (2 to 11 months of age) ; ≥ 40/minute (12 months of age or above) ;
The highest value during the course of the illness will be used.

⁴ RSV infection confirmed on nasal swab positive for RSV A or B by quantitative Reverse Transcription Polymerase Chain Reaction (qRT-PCR).

⁵ RSV sampling and testing is based on medical judgment of medical practitioner or driven by algorithm.

⁶ Hospitalization is defined as a medical decision that the infant requires admission for observation or treatment.

- For the analysis of RTI episode, a new RTI episode will be defined as any occurrence of cough, runny nose, blocked nose, wheezing or difficulty breathing with an interval of at least 7 symptom free days since the last episode of RTI that was diagnosed.
- For molecular biology (qRT-PCR test), the following cut-off will be applied: -

System	Component	Method	Unit	Cut-off
Nasal swab	RSV-A RNA	Quantitative real-time PCR (qRT-PCR)	Copies/ml	1.12 X 10 ³
Nasal swab	RSV-B RNA	Quantitative real-time PCR (qRT-PCR)	Copies/ml	1.47 x 10 ³

